13.1.2 Analysis of Demographics and Other Baseline Characteristics

Demographic and other baseline characteristic data will be summarized for all enrolled subjects by treatment sequence, and overall. Summary statistics (eg, number of subjects, mean, median, SD, and range) will be generated for continuous variables (eg, age and weight) and the number and percentage of subjects within each category will be presented for categorical variables (eg, sex, ethnicity, race, smoking status).

Demographic data and reasons for screen failure will be summarized overall for subjects who are screened but not enrolled in the study. Individual demographic data, date of informed consent, and reason for screen failure will be listed.

13.1.3 PK Analysis

13.1.3.1 TAK-831 Concentrations in Plasma

For each regimen, TAK-831 plasma concentrations will be summarized using descriptive statistics (mean, median, SD, %CV, minimum, and maximum) for each scheduled sampling time. Individual subject plasma concentration data will be listed.

13.1.3.2 Plasma PK Parameters

For each regimen, TAK-831 plasma PK parameter estimates will be summarized using descriptive statistics (N, mean, median, SD, %CV, minimum, and maximum). In addition, geometric means will be calculated for C_{max} and AUCs. Individual subject plasma PK parameter data will be listed.

Analysis of variance models will be performed on TAK-831 $\ln C_{max}$ and $\ln AUCs$. The model will include sequence, period, and regimen as fixed factors and subject-within-sequence as a random factor. Pairwise comparisons between the test regimen (Regimen B: fed state) and the reference regimen (Regimen A: fasted state) will be made and the 2-sided 90% CIs for the ratio of the central values for C_{max} and AUCs between regimens (Test: Reference) will be constructed to estimate the effect of food on TAK-831 PK.

Additional statistical analyses will be performed as appropriate.

13.1.4 PD Analysis

13.1.4.1 CCI [Redacted]

CCI [Redacted]

13.1.4.2 Plasma PD Parameters

CCI [Redacted]

Additional statistical or PK/PD analyses will be performed as appropriate.

13.1.5 Safety Analysis

No statistical testing will be performed or inferential statistics will be generated.

13.1.5.1 AEs

All AEs will be coded by system organ class (SOC) and preferred term (PT) using MedDRA. TEAEs with onset occurring within 30 days (onset date – last date of dose +1≤30) after the last dose of study drug will be included in the summary tables. TEAEs will be summarized by SOC and PT with descriptive statistics (N and percentage of subjects). The following summary tables will be generated by regimen: all TEAEs, all drug-related TEAEs, relationship of TEAEs to study drug (related vs not related), severity of TEAEs, and severity of related TEAEs. Data listings will be provided for all AEs including PTE, TEAEs, AEs leading to death, AEs leading to study drug or study visit discontinuation, and SAEs.

13.1.5.2 Clinical Laboratory Evaluations

Individual clinical laboratory test data (hematology, chemistry, and urinalysis) will be listed for all subjects. Baseline, postdose, and changes from Baseline to postdose data will be summarized by regimen for each scheduled time point using descriptive statistics. The Baseline for each regimen is defined as the last observation prior to the dose of study drug. Individual clinical laboratory test results that meet Takeda's markedly abnormal criteria (as defined in the SAP) will be listed and summarized by regimen.

13.1.5.3 Vital Signs

Individual vital sign data (oral temperature, respiration rate, blood pressure, and heart rate) will be listed for all subjects. Baseline, postdose, and changes from Baseline to postdose data will be summarized by regimen for each scheduled time point using descriptive statistics. The Baseline for each regimen is defined as the last observation prior to the dose of study drug. Individual vital sign results that meet Takeda's markedly abnormal criteria (as defined in the SAP) will be listed and summarized by regimen.

13.1.5.4 ECGs

Individual quantitative 12-lead ECG data will be listed for all subjects. Baseline, postdose, and changes from Baseline in quantitative ECG data will be summarized by regimen for each scheduled time point using descriptive statistics. The baseline is defined as the last observation prior to the dose of study drug. Individual ECG results that meet Takeda's markedly abnormal criteria (as defined in the SAP) will be listed and summarized by regimen.

13.1.5.5 Other Variables

Individual physical examination findings will be listed for all subjects.

13.2 Interim Analysis and Criteria for Early Termination

No interim analysis is planned.

13.3 Determination of Sample Size

With a sample size of 16 subjects (8 subjects per treatment sequence), allowing for a maximum of 2 dropouts, a 2-sided 90% CI for the difference in the paired means of the $\ln C_{\max}$ will extend 0.23 from the observed mean. Assuming a point estimate of the food effect of 2 (observed ratio of fed vs fasting $C_{\max}=2$), which means food increases C_{\max} by 100%, this should lead to a lower bound of the 90% CI of 1.589 (58.9% increase) and an upper bound of the 90% CI of 2.517 (151.7% increase) for the ratios of the C_{\max} central values (fed/fast). In addition, when a central value ratio of 1 is observed, the 90% CI should be approximately (-0.79, 1.26). This calculation also assumes the intrasubject %CV for C_{\max} is 37.5%, which is estimated from Study TAK-831-1001 (Part 4).

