7.6 Procedures for Discontinuation or Withdrawal of a Subject

The investigator may discontinue a subject's study participation at any time during the study when the subject meets the discontinuation criteria described in Section 7.5. In addition, a subject may discontinue his or her participation without giving a reason at any time during the study. Should a subject's participation be discontinued, the primary criterion for termination must be recorded by the investigator. In addition, efforts should be made to perform all procedures scheduled for the Early Termination Visit. Discontinued or withdrawn subjects may be considered for replacement on a case by case basis.

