13.1.1 Analysis Sets

Safety Analysis Set

The safety analysis set will consist of all enrolled subjects who received at least 1 dose of study drug. Subjects in this analysis set will be used for demographic, other baseline characteristic, and safety summaries.

PK Analysis Set

The PK analysis set will consist of subjects from the safety set who have at least 1 measurable postdose TAK-831 plasma concentration.

PD Analysis Set

CCI

If any subjects are found to have incomplete data, a decision will be made on a case-by-case basis as to their inclusion in the analysis; however, all data will be presented in the subject listings.

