### 7.9.2 Plasma Pharmacokinetic Parameters

The pharmacokinetic (PK) parameters of TAK-831 will be determined from the concentration-time profiles for all evaluable subjects. Actual sampling times, rather than scheduled sampling times, will be used in all computations involving sampling times. The following PK parameters will be calculated from the plasma concentration values of TAK-831 using non-compartmental analysis using Phoenix WinNonLin (version 6.3 or higher):  $AUC_{last}$ ,  $AUC_{\infty}$ ,  $C_{max}$ ,  $CL/F$ ,  $\lambda_z$ ,  $t_{1/2z}$ ,  $t_{max}$  and  $V_z/F$ .

Additional parameters may be calculated if necessary.

For each regimen, descriptive statistics (N, mean, median, SD, %CV, minimum, and maximum) will be used to summarize TAK-831 plasma PK parameters. In addition, geometric means will be calculated for  $C_{max}$  and AUCs. Individual subject plasma PK parameter data will be listed.

Statistical inference to estimate the food effect on TAK-831 PK will be performed using an analysis of variance (ANOVA) model on TAK-831  $\ln C_{max}$  and  $\ln AUCs$ . The models will include sequence, period, and regimen as fixed factors and subject-within-sequence as a random factor. Difference between the test regimen (Regimen B: fed state) and the reference regimen (Regimen A: fasted state) will be calculated using the least square (LS) means and 90% C.Is.

To evaluate the effect of food on TAK-831 PK, the central value ratios and the 2-sided 90% CIs for the ratio of the central values for  $C_{max}$  and AUCs between the two regimens will be obtained as the antilog of the difference of the least squares (LS) means on a natural logarithm scale, and the 90% CIs will be obtained by taking the antilog of the 90% CI for the difference between the LS means on the natural logarithmic scale.

Alternative statistical analyses will be used if deemed appropriate.

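### The stated 90% CI half-width of 0.23 for ln(Cmax) is too narrow for the two dropouts it allows: the planned crossover ANOVA on 14 complete pairs gives about 0.244

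*Protocol*

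**What the plan says.** Protocol 13.3 opens "With a sample size of 16 subjects (8 subjects per treatment sequence), allowing for a maximum of 2 dropouts". It then says that "a 2-sided 90% CI for the difference in the paired means" of ln(Cmax) "will extend 0.23 from the observed mean". At an observed fed/fasted ratio of 2 it gives limits of 1.589 and 2.517. The intrasubject CV is taken as 37.5%, from Part 4 of Study TAK-831-1001. The Study Summary and SAP 6.0 repeat this text. None of the three names the quantile, the degrees of freedom or the number of completers behind 0.23.

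The analysis is fixed elsewhere. Protocol 13.1.3.2 says "The model will include sequence, period, and regimen as fixed factors and subject-within-sequence as a random factor", and SAP 7.9.2 specifies the same model. The SAP adds that the "90% CIs will be obtained by taking the antilog of the 90% CI for the difference between the LS means" on the log scale.

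Two further provisions bear on dropouts. Under Protocol 13.1.1, "The PK analysis set will consist of subjects from the safety set who have at least 1 measurable postdose TAK-831 plasma concentration", so a subject with Period 1 data only can stay in the set. Under Protocol 7.6, "Discontinued or withdrawn subjects may be considered for replacement on a case by case basis".

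**The concern.** The natural reading of 13.3 is that 0.23 is the precision left after the two allowed dropouts, under the analysis the trial will run. In a two-sequence, two-period crossover ANOVA with n complete pairs, the regimen contrast is tested on n - 2 error df, so 14 pairs leave 12. The t quantile on 12 df is 1.782 against a normal quantile of 1.645, a difference of about 8%, and that is enough to move the half-width away from 0.23.

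The half-width is the only argument given for the sample size; 13.3 contains no power or equivalence criterion. If it describes a different number of completers or a different quantile, the stated precision is better than the design delivers in the case it claims to cover.

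**Working it through.** **Inputs.** 16 subjects, 8 per sequence, at most 2 dropouts, 90% two-sided CI and CV 37.5% (Protocol 13.3). Model and interval as in Protocol 13.1.3.2 and SAP 7.9.2.

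**Within-subject log SD.** σ_w² = ln(1 + 0.375²) = 0.1316, so σ_w = 0.3627.

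**Formula.** SE = σ_w × √[½(1/n₁ + 1/n₂)], where n₁ and n₂ are the complete pairs per sequence. Half-width = quantile × SE.

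**The plan's own figure.** 2 × exp(−0.23) = 1.589 and 2 × exp(+0.23) = 2.517, so the stated limits follow from 0.23. These routes lead to 0.23:

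| Completers | Quantile | SE | Half-width |
|---|---|---|---|
| 16 (8/8) | t, 14 df: 1.761 | 0.1282 | 0.226 |
| 14 (7/7) | normal: 1.645 | 0.1371 | 0.2255 |
| 14 (7/7) | t, 26 df: 1.706 | 0.1371 | 0.234 |

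The first has no dropouts. The other two use a quantile that the planned model does not have. If 37.5% is read directly as the log-scale SD, 0.233 results from 14 completers with the normal quantile or from 16 with t on 14 df. With 14 completers and t on 12 df that reading gives 0.253, further from 0.23.

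**The planned ANOVA on complete pairs.**

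| Completers | df | t | SE | Half-width | 90% CI at ratio 2 | 90% CI at ratio 1 |
|---|---|---|---|---|---|---|
| 16 (8/8) | 14 | 1.761 | 0.1282 | 0.226 | 1.60 to 2.51 | 0.80 to 1.25 |
| 15 (8/7) | 13 | 1.771 | 0.1327 | 0.235 | 1.58 to 2.53 | 0.79 to 1.27 |
| 14 (7/7) | 12 | 1.782 | 0.1371 | 0.244 | 1.57 to 2.55 | 0.78 to 1.28 |
| 14 (8/6) | 12 | 1.782 | 0.1385 | 0.247 | 1.56 to 2.56 | 0.78 to 1.28 |

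Against 0.23, the last two rows are 0.2444/0.23 = 1.06 and 0.2469/0.23 = 1.07. A simple paired t analysis of 14 pairs (13 df) gives 1.771 × 0.1371 = 0.243, so dropping the period term does not recover 0.23 either.

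**CV that would make 0.23 right with 14 pairs.** σ_w = 0.23 / (1.782 × √(1/7)) = 0.3414, so CV = √(exp(0.3414²) − 1) = 35.2%, not 37.5%.

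**Dropouts kept with Period 1 data only.** With subject random, such subjects add a little between-subject information. How much depends on the between-subject variance, which the documents do not give for the T2 tablet, so it was varied from near zero to very large as an assumption. The documents also name no df method.

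| Dropout pattern | 12 df held | Satterthwaite df |
|---|---|---|
| One per sequence (7/7) | 0.237 to 0.244 | 0.235 to 0.244 |
| Both in one sequence (8/6) | 0.238 to 0.247 | 0.236 to 0.247 |

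Only the lowest corner rounds to 0.23: 0.2346, with one dropout per sequence, near-zero between-subject variance and Satterthwaite df.

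**The case against.** The strongest reply is that 0.23 does allow for the dropouts: 14 completers with a normal quantile give 0.2255, and a known-SD formula is a common planning shortcut. Since 13.3 names no quantile, the text does not contradict itself. That explains where the number may come from, but the reported interval will use an estimated variance on 12 df, so the shortcut understates the width by about 8% before rounding.

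Second, 0.244 is itself a planning value. If the assumed variance is true, the realised half-width with 7/7 pairs and 12 df has mean 0.239, median 0.238 and an 80% range of 0.177 to 0.304, and it is 0.23 or less about 44% of the time. So the gap of 0.014 is small against sampling spread. This stands as a reason for low severity. It does not support 0.23, because even the mean rounds to 0.24.

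Third, two lost pairs is the upper limit. Dropouts may be replaced. A subject who leaves late in Period 2 may already have supplied both Cmax values, since Cmax needs only the early samples. With 16 pairs the plan does slightly better than stated. All of this is correct, and 0.23 lies inside the overall range of 0.226 to 0.247. But replacement is discretionary, and 13.3 presents 0.23 as holding with the dropouts, not as depending on their being replaced or leaving late.

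**Conclusion.** The concern holds, as a minor point. For the case that 13.3 says it covers, the planned analysis gives a half-width of about 0.244 (0.247 if both dropouts fall in one sequence), not 0.23. That is 6 to 7% wider on the log scale, and at a ratio of 2 the limits move from 1.589 and 2.517 to about 1.57 and 2.55.

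This rests on a CV of 37.5% converted to a log SD of 0.3627, two unreplaced dropouts that contribute no within-subject contrast, and t on 12 df. Retaining Period 1 data narrows the result to no less than 0.235.

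The stated figure is not an arithmetic slip; it describes either full completion or a different quantile. The consequence is limited to how the precision is described. The aim is estimation, no acceptance limit depends on the width, and nothing here calls N = 16 into question.

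**What to change.** In Protocol 13.3, the Study Summary and SAP 6.0, replace 0.23 and its limits with about 0.244 for 14 completers: 1.57 to 2.55 at a ratio of 2, and 0.78 to 1.28 at a ratio of 1. Replacing the ratio-1 limits also removes the impossible minus sign now printed before 0.79. Optionally add the 16-completer case: 0.226, with 1.60 to 2.51 at a ratio of 2 and 0.80 to 1.25 at a ratio of 1.

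State that the calculation uses the t quantile on completers minus 2 df, give the number of completers, and say that dropouts are assumed to contribute no within-subject contrast.

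The cost is wording in three places and a slightly less favourable stated precision. The sample size, design and analysis do not change.

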14.0 QUALITY CONTROL AND QUALITY ASSURANCE

14.1 Study-Site Monitoring Visits

Monitoring visits to the study site will be made periodically during the study to ensure that all aspects of the protocol are followed. Source documents will be reviewed for verification of data recorded on the eCRFs. Source documents are defined as original documents, data, and records. The investigator and study site guarantee access to source documents by the sponsor or its designee (contract research organization) and by the IRB.

All aspects of the study and its documentation will be subject to review by the sponsor or the sponsor's designee, including but not limited to the Investigator's Binder, study drug, subject medical records, informed consent documentation, documentation of subject authorization to use personal health information (if separate from the informed consent forms), and review of eCRFs and associated source documents. It is important that the investigator and other study personnel are available during the monitoring visits and that sufficient time is devoted to the process.

14.2 Protocol Deviations

The investigator should not deviate from the protocol, except where necessary to eliminate an immediate hazard to study subjects. Should other unexpected circumstances arise that will require deviation from protocol-specified procedures, the investigator should consult with the sponsor or designee (and IRB, as required) to determine the appropriate course of action. There will be no exemptions (a prospectively approved deviation) from the inclusion or exclusion criteria.

The site should document all protocol deviations in the subject's source documents, where applicable. In the event of a significant deviation, the site should notify the sponsor or its designee (and IRB, as required). Significant deviations include, but are not limited to, those that involve fraud or misconduct, increase the health risk to the subject, or confound interpretation of primary study assessment. A Protocol Deviation Form should be completed by the site and signed by the sponsor or designee for any significant deviation from the protocol.

The investigator should document all protocol deviations.

Every attempt will be made to collect each PK and PD blood sample at the designated time point, and the actual time of each blood sample will be recorded on the source document and eCRF. Blood samples not collected within the window specified for the scheduled sample time should be reported to Takeda using the Protocol Deviation Form. Protocol Deviation Forms are to be completed for PK/PD samples collected outside of the windows defined in [Table 14.a](#).

Table 14.a Windows for PK and PD Blood Sample Collection

Minutes	Nominal Sampling Time
≤30 minutes predose	0 hour
±5	immediately postdose to ≤6 hours
±10	>6 hours to ≤12 hours postdose
±15	>12 hours to ≤24 hours
±30	>24 hours

14.3 Quality Assurance Audits and Regulatory Agency Inspections

The study site also may be subject to quality assurance audits by the sponsor or designees. In this circumstance, the sponsor-designated auditor will contact the site in advance to arrange an auditing visit. The auditor may ask to visit the facilities where laboratory samples are collected, where the medication is stored and prepared, and any other facility used during the study. In addition, there is the possibility that this study may be inspected by regulatory agencies, including those of foreign governments (eg, the FDA, the United Kingdom Medicines and Healthcare products Regulatory Agency [MHRA], the Pharmaceuticals and Medical Devices Agency of Japan). If the study site is contacted for an inspection by a regulatory body, the sponsor should be notified immediately. The investigator and study site guarantee access for quality assurance auditors to all study documents as described in Section 14.1.

15.0 ETHICAL ASPECTS OF THE STUDY

This study will be conducted with the highest respect for the individual participants (ie, subjects) according to the protocol, the ethical principles that have their origin in the Declaration of Helsinki, and the ICH Harmonised Tripartite Guideline for GCP. Each investigator will conduct the study according to applicable local or regional regulatory requirements and align his or her conduct in accordance with the “Responsibilities of the Investigator” that are listed in [Appendix B](#). The principles of Helsinki are addressed through the protocol and through appendices containing requirements for informed consent and investigator responsibilities.

15.1 IRB Approval

IRBs must be constituted according to the applicable requirements of each participating region. The sponsor or designee will require documentation noting all names and titles of members who make up the respective IRB. If any member of the IRB has direct participation in this study, written notification regarding his or her abstinence from voting must also be obtained. Those Americas sites unwilling to provide names and titles of all members because of privacy and conflict of interest concerns should instead provide a Federal Wide Assurance Number or comparable number assigned by the Department of Health and Human Services.

The sponsor or designee will supply relevant documents for submission to the respective IRB for the protocol’s review and approval. This protocol, the Investigator’s Brochure, a copy of the informed consent form, and, if applicable, subject recruitment materials and/or advertisements and other documents required by all applicable laws and regulations, must be submitted to a central or local IRB for approval. The IRB’s written approval of the protocol and subject informed consent must be obtained and submitted to the sponsor or designee before commencement of the study (ie, before shipment of the sponsor-supplied drug or study-specific screening activity). The IRB approval must refer to the study by exact protocol title, number, and version date; identify versions of other documents (eg, informed consent form) reviewed; and state the approval date. The sponsor will notify the study site once the sponsor has confirmed the adequacy of site regulatory documentation and, when applicable, the sponsor has received permission from competent authority to begin the study. Until the site receives notification no protocol activities, including screening, may occur.

Study sites must adhere to all requirements stipulated by their respective IRB. This may include notification to the IRB regarding protocol amendments, updates to the informed consent form, recruitment materials intended for viewing by subjects, local safety reporting requirements, reports and updates regarding the ongoing review of the study at intervals specified by the respective IRB, and submission of the investigator’s final status report to the IRB. All IRB approvals and relevant documentation for these items must be provided to the sponsor or its designee.

Subject incentives should not exert undue influence for participation. Payments to subjects must be approved by the IRB and sponsor.

15.2 Subject Information, Informed Consent, and Subject Authorization

Written consent documents will embody the elements of informed consent as described in the Declaration of Helsinki and the ICH Guidelines for GCP and will be in accordance with all applicable laws and regulations. The informed consent form, subject authorization form (if applicable), and subject information sheet (if applicable) describe the planned and permitted uses, transfers, and disclosures of the subject's personal and personal health information for purposes of conducting the study. The informed consent form and the subject information sheet (if applicable) further explain the nature of the study, its objectives, and potential risks and benefits, as well as the date informed consent is given. The informed consent form will detail the requirements of the participant and the fact that he or she is free to withdraw at any time without giving a reason and without prejudice to his or her further medical care.

The investigator is responsible for the preparation, content, and IRB approval of the informed consent form and if applicable, the subject authorization form. The informed consent form, subject authorization form (if applicable), and subject information sheet (if applicable) must be approved by both the IRB and the sponsor prior to use.

The informed consent form, subject authorization form (if applicable), and subject information sheet (if applicable) must be written in a language fully comprehensible to the prospective subject. It is the responsibility of the investigator to explain the detailed elements of the informed consent form, subject authorization form (if applicable), and subject information sheet (if applicable) to the subject. Information should be given in both oral and written form whenever possible and in the manner deemed appropriate by the IRB. In the event the subject is not capable of rendering adequate written informed consent, then the subject's legally acceptable representative may provide such consent for the subject in accordance with applicable laws and regulations.

The subject, or the subject's legally acceptable representative, must be given ample opportunity to: (1) inquire about details of the study and (2) decide whether or not to participate in the study. If the subject, or the subject's legally acceptable representative, determines he or she will participate in the study, then the informed consent form and subject authorization form (if applicable) must be signed and dated by the subject, or the subject's legally acceptable representative, at the time of consent and prior to the subject entering into the study. The subject or the subject's legally acceptable representative should be instructed to sign using their legal names, not nicknames, using blue or black ballpoint ink. The investigator must also sign and date the informed consent form and subject authorization (if applicable) at the time of consent and prior to subject entering into the study; however, the sponsor may allow a designee of the investigator to sign to the extent permitted by applicable law.

Once signed, the original informed consent form, subject authorization form (if applicable), and subject information sheet (if applicable) will be stored in the investigator's site file. The investigator must document the date the subject signs the informed consent in the subject's medical record. Copies of the signed informed consent form, the signed subject authorization form (if applicable), and subject information sheet (if applicable) shall be given to the subject.

All revised informed consent forms must be reviewed and signed by relevant subjects or the relevant subject's legally acceptable representative in the same manner as the original informed consent. The date the revised consent was obtained should be recorded in the subject's medical record, and the subject should receive a copy of the revised informed consent form.

Subjects who consented and provided a PGx sample for DNA analysis can withdraw their consent and request disposal of a stored sample at any time prior to analysis. Notify the sponsor of consent withdrawal.

